This is a Phase 3 multi-center, randomized, double-blind, vehicle-controlled, parallel group study to be conducted in approximately 850 subjects with MC. After obtaining informed consent/assent, subjects who satisfy entry criteria will be randomized 1:1 (active:vehicle) using an interactive web response system. Subjects receiving current treatment for MC at the time of the Screening Visit will enter a washout period of up to 14 days prior to randomization. In the event no washout period is required, Screening and Baseline visit activities may be combined into a single in-clinic visit. At randomization, subjects will be stratified by investigator type (dermatologist vs other), the subject's beginning-of-the-end (BOTE) Inflammation Score at Baseline (no inflammation [BOTE=0] vs mild/moderate/severe/very severe inflammation [BOTE $\geq$ 1]) and number of randomly assigned subjects per household (1 subject per household vs 2 subjects per household). Subjects will be stratified to 5 strata first by subjects per household. Subjects from 1-subject households will be stratified by investigator type and baseline BOTE score. Subjects from 2-subject households will not be further stratified with respect to investigator type and baseline BOTE score because the overall sample that is expected for the stratum for households with two subjects is not large enough to support further stratification.

A maximum of two subjects from the same household may be randomized into the study. They must be randomized on the same day and both must individually meet all inclusion/no exclusion criteria. For subjects in the same household, Screening can occur on different days; however, the Baseline visit must occur on the same day. Households randomizing two subjects will receive the same treatment assignment for both subjects.

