## 5. DETERMINATION OF SAMPLE SIZE

Approximately 850 subjects, 6 months of age and older, with a minimum of 3 and a maximum of 70 MC lesions at Baseline will be randomized in a 1:1 (active:vehicle) scheme. The sample size assumptions for this study were informed by the integration of the completed phase 3 studies [NI-MC301](#) and [NI-MC302](#). Multiple replications of simulated random sampling of the integrated NI-MC301 and NI-MC302 data was performed to ensure the sample size assumptions align with the proposed design of NI-MC304. This includes the 1:1 ratio (active:vehicle) and the percentages observed in NI-MC301 and NI-MC302 for each stratum of each of the stratification factors: investigator type, number of randomized subjects per household, and baseline BOTE score that are planned for NI-MC304.

The analysis of the proportion of subjects with complete response of all treatable MC at Week 12 within the Intent-to-Treat (ITT) Population of the multiple replications of simulated random sampled integrated data yields rates of 20% for vehicle and 29.5% for SB206 10.3% QD with the covariate-adjusted treatment difference was 9.5%. A sample size of 850 subjects (425 subjects in the SB206 10.3% QD group and 425 subjects in the vehicle group) will provide 90% power for a 2-sided alpha test of size 0.05 to detect an absolute difference of 9.5% when the vehicle response rate is 20%.

Simulations were performed with 10,000 replications to confirm the accuracy of these power estimates (i.e., true power and simulation based estimate of power) and to provide simulated median, 10% percentile and lowest detectable treatment difference estimates for a sample size of 850 subjects.

At the two-sided  $\alpha=0.05$  level, the median detectable treatment difference is approximately 9.9% with a simulation based estimated power of 88%. The tenth percentile for detectable treatment difference is 7.1%, thus approximately 90% of the simulations with two-sided  $p < 0.05$

produced an estimated treatment difference exceeding 7.1%. The lowest detectable treatment difference is 5.7%.

At two-sided alpha levels  $<0.05$ , for example,  $p=0.025$  level, the median detectable treatment difference is approximately 10.2% with a simulation based estimated power of 82%. The tenth percentile for detectable treatment difference is 7.7% and a lowest detectable difference of 6.5%.

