## 10.3 Adjustments for Covariates

The model for the primary efficacy will include adjustments for the following covariates: investigator type (dermatologist vs other), household number of randomized subjects (1 subject per household vs 2 subjects per household), BOTE score at Baseline (no inflammation [BOTE=0] vs mild/moderate/severe/very severe inflammation [BOTE $\geq$ 1]), age (0 to <3, 3 to <4, 4 to <5, 5 to <6, 6 to <7, 8 to <9, 9 to <12, and  $\geq$ 12 years old), and baseline lesion count. If there are not at least 3 responders and non-responders at each level of the stratification factors, then that stratification factor will be removed from the model. If there are fewer than 10 responders/non-responders, then neither investigator type nor household number of randomized subjects nor BOTE score at Baseline will be included in the model.

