## 10.4 Handling of Dropouts or Missing Data

In analyses based on response, a missing response will be considered a non-responder.

For a sensitivity analysis, subjects with missing lesion count at Week 12 but who demonstrated complete clearance at the last collected lesion assessment will be counted as responders.

An additional sensitivity analysis using multiple imputation will be performed to address subjects with missing lesion count at Week 12. A monotone imputation model will be utilized in the following steps:

1. The lesion count data will be imputed to follow a monotone missing data pattern using the Markov chain Monte Carlo method for 10 imputations.
2. Each of the 10 imputations will then be imputed a further 10 times using a monotone regression method to impute the remaining missing data and the Week 12 lesion count using lesion count assessments at Weeks 2, 4, and 8, treatment group, investigator type (dermatologist vs other), BOTE score at Baseline (no inflammation [BOTE=0] vs mild/moderate/severe/very severe inflammation [BOTE $\geq$ 1]), age (0 to <3, 3 to <4, 4 to <5, 5 to <6, 6 to <7, 8 to <9, 9 to <12, and  $\geq$ 12 years old), and baseline lesion count as covariates.

3. Complete Clearance at Week 12 will be re-derived based on the imputed values and then analyzed using the primary analysis model. The results of the 100 analyses will be transformed into a normal statistic and combined into a single analysis using PROC MIANALYZE.

The ROUND and MINIMUM options will be utilized in Steps 1 and 2 to ensure imputed values are non-negative integers. The seed to be used is 20200727.

For subjects with a missing lesion count at Week 12 and identified as “Lost to Follow-up” by the investigator, the following sensitivity analysis will be performed. These lost to follow-up subjects will be contacted to obtain a patient reported outcome of MC disease status at the end of their study participation of either ‘Resolved (no lesions left)’, ‘Resolving (number of lesions decreasing)’, ‘Unchanged (number of lesions similar to previous clinic visit)’, or ‘Worsening (number of lesions increased)’. A reported response endpoint will be derived in the following manner:

- If a subject has a Week 12 lesion count assessment, then the subject will be deemed a responder if the count was 0.

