The  $p_{SB206}$  and  $p_{Vehicle}$  are the transformed predicted log odds at the mean of the covariates,  $s^2$ 's are the standard errors of the predicted log odds and the odds ratio.

As a sensitivity analysis, the above primary analysis model will be applied to the PP Population. An additional sensitivity analysis counting subjects who discontinued prior to Week 12 or have a missing lesion count assessment but who demonstrated complete clearance at the last collected lesion assessment as responders will be presented. The impact of mis-stratifications may be explored via a sensitivity analysis.

An analysis where the complete clearance response probability for each dropout prior to Week 12 will be independently generated across the following scenarios (Vehicle response probability, SB206 response probability):

(0.1, 0.1)	(0.1, 0.0)			
(0.2, 0.2)	(0.2, 0.1)	(0.2, 0.0)		
(0.3, 0.3)	(0.3, 0.2)	(0.3, 0.1)	(0.3, 0.0)	
(0.4, 0.4)	(0.4, 0.3)	(0.4, 0.2)	(0.4, 0.1)	(0.4, 0.0)

The analysis will be produced 100 times and then the results for the estimated log odds ratio for treatment and its estimated standard error from each of the imputations will be combined using PROC MIANALYZE.

An additional sensitivity analysis will be performed in a subset of the ITT population where only 1 subject from each household is chosen to contribute to the model based on the subject with the highest number of baseline treatable MC and the oldest to break ties, if needed. A logistic regression model including treatment, investigator type, BOTE score at Baseline, age, and baseline lesion counts will be utilized.

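### The one-subject-per-household check and the multiple-imputation regression leave out household size, a randomization stratum and primary-model covariate; the effect is very small and the correction costs one term in each

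*SAP*

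**What the plan says.** **Randomization.** SAP section 4 states: "Subjects will be stratified to 5 strata first by subjects per household". Only one-subject households are then split by investigator type and baseline BOTE score. Two subjects from one household receive the same treatment.

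**Primary model.** SAP 10.3 lists among its covariates "household number of randomized subjects (1 subject per household vs 2 subjects per household"; SAP 11.1 codes this as a 0/1 indicator, and Protocol 10.3.1 agrees.

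**One-subject-per-household check (SAP 11.1).** One subject is kept from each household: the one with the most treatable lesions at baseline, with ties going to the older. The model is then: "A logistic regression model including treatment, investigator type, BOTE score at Baseline, age, and baseline lesion counts will be utilized". Household size is not listed.

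**Multiple imputation (SAP 10.4).** Step 2 fills the gaps left after step 1 and names its target and predictors: "the Week 12 lesion count using lesion count assessments at Weeks 2, 4, and 8, treatment group, investigator type (dermatologist vs other), BOTE score at". The BOTE score meant is the one at baseline, and the list ends with age group and baseline lesion count. Household size is not listed. Step 3 re-derives clearance from the imputed counts and fits the primary analysis model, which does contain it.

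The SAP gives no reason for either omission.

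**The concern.** The one-per-household check asks whether the primary result depends on how household pairs are handled. Dropping the second member and replacing the GEE with ordinary logistic regression both follow from that question. Dropping a stratification covariate does not. If the check and the primary result differ, the covariate change is a second possible source.

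In the multiple imputation, the imputation regression lacks a variable that the analysis model uses. Given the other predictors, missing counts are drawn as if household size had no association with the count, and a model that estimates that association is then fitted. The usual practice is for the imputation model to contain at least the covariates of the analysis model.

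What is at stake is how cleanly two supportive analyses can be read. The primary test, its error rate and its power are untouched.

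**Working it through.** **1. The plan's own figure.** SAP section 5: "A sample size of 850 subjects (425 subjects in the SB206 10.3% QD group and 425 subjects in the vehicle group" (parenthesis closed in the source), rates "yields rates of 20% for vehicle and 29.5% for SB206 10.3% QD", and a design that "will provide 90% power for a 2-sided alpha test of size 0.05 to detect an absolute difference of 9.5" percentage points.

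- Pooled rate (0.200 + 0.295)/2 = 0.2475. SE under H0 = √(2 × 0.2475 × 0.7525/425) = 0.02960. SE under H1 = √((0.2 × 0.8 + 0.295 × 0.705)/425) = 0.02942.
- Power = Φ[(0.095 − 1.96 × 0.02960)/0.02942] = Φ(1.26) = 89.6%. With unpooled variance, Φ(0.095/0.02942 − 1.96) = 89.8%. The stated 90% is reproduced.
- Implied odds ratio (0.295/0.705)/(0.20/0.80) = 1.67; log odds ratio 0.515.

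**2. The covariate lists side by side.**

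| Model | Household size |
|---|---|
| Primary GEE (SAP 10.3, 11.1) | included |
| Center-pool logistic model (SAP 10.8) | included |
| Mixed models for lesion change (SAP 11.2, 11.3) | included, through the primary covariates |
| Mixed model on baseline BOTE (SAP 12) | included |
| MI step 3 analysis (SAP 10.4) | included, through the primary model |
| MI step 2 imputation (SAP 10.4) | **omitted** |
| One subject per household (SAP 11.1) | **omitted** |

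**3. Can the term still be fitted after selection?** Yes. Selection removes the clustering, so the repeated statement is no longer needed. The one-versus-two indicator is a fixed effect that still varies between retained subjects.

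**4. Size in the one-per-household model.** The documents do not give the number of two-subject households, so 5%, 15% and 30% of subjects are assumed. The household-size odds ratio is assumed to be 0.5, 1 or 2. Other settings: allocation balanced within the household-size stratum, treatment odds ratio 1.67, baseline lesion count (mean 18) in the model, 600 replicates per row. Households retained = 850 × (1 − share/2).

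| Share | Household OR | Households | Log OR with term | Without | Mean absolute difference | SE (with) | p<0.05 verdict differs |
|---|---|---|---|---|---|---|---|
| 5% | 0.5 | 829 | 0.5243 | 0.5243 | 0.0012 | 0.164 | 0% |
| 5% | 1 | 829 | 0.5221 | 0.5216 | 0.0011 | 0.164 | 0% |
| 5% | 2 | 829 | 0.5253 | 0.5209 | 0.0045 | 0.164 | 0.2% |
| 15% | 0.5 | 786 | 0.5117 | 0.5087 | 0.0033 | 0.169 | 0% |
| 15% | 1 | 786 | 0.5165 | 0.5158 | 0.0009 | 0.169 | 0.2% |
| 15% | 2 | 786 | 0.5163 | 0.5112 | 0.0052 | 0.169 | 0.8% |
| 30% | 0.5 | 722 | 0.5125 | 0.5064 | 0.0064 | 0.176 | 1.0% |
| 30% | 1 | 722 | 0.5260 | 0.5252 | 0.0010 | 0.176 | 0% |
| 30% | 2 | 722 | 0.5162 | 0.5070 | 0.0093 | 0.177 | 0.5% |

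The largest shift is 0.0093/0.177, about 5% of one standard error. Power differs by at most 0.8 points. A further simulation built in the choice of the higher-count member (30 to 100 pairs, household log-odds effect −1.0 to +0.7). It gave shifts of 0.001 to 0.007 against a standard error of 0.17 to 0.18, with the verdict changing in at most 1% of replicates.

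The subset itself lowers power to about 88.8%, 87.1% or 84.2% at the three shares. That loss comes from having fewer subjects, not from the missing covariate.

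**5. Size in the multiple imputation.** Study discontinuation was 15.3% and 17.2% in the two completed phase 3 trials (Protocol 2.1). If missing Week 12 counts ran at that level regardless of household size, those from two-subject households would number about 850 × 0.05 × 0.153 ≈ 7 to 850 × 0.30 × 0.172 ≈ 44. One illustrative simulation assumed 16% missing, 30 to 100 pairs and a treatment log odds ratio of about 0.94, larger than planned. The treatment estimate moved by 0.001 to 0.010 against a standard error of about 0.20. The documents give no missingness by household size, so this is only an indication.

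**6. Sparsity.** At shares of 5%, 15% and 30%, about 21, 64 and 128 retained subjects come from two-subject households. At the pooled 24.75% rate that is about 5, 16 and 32 responders. With a household odds ratio of 0.5 applied to that rate, the response is 0.1645/1.1645 = 14.1%, or about 3 responders among 21. The SAP 10.3 rule requires at least 3 responders and 3 non-responders per level, so at the low end it could come into play.

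**The case against.** The strongest reply is that this makes no practical difference. Allocation is balanced within the stratum, so omitting the term does not confound the treatment effect. What remains is mainly the slight shrinkage of an odds ratio when a prognostic covariate is dropped, and the simulations put it at a small fraction of a standard error. No visible gap between the check and the primary result could sensibly be blamed on this term. That stands, and it limits the point to a minor improvement.

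Second, the documents nowhere say that a sensitivity analysis may change only one thing, and removing household structure altogether is a defensible stress test. That would be a fair reason, but the SAP does not give it, and its other adjusted models keep the factor.

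Third, keeping one member per pair halves the subjects in a stratum the SAP already calls too small for further stratification. This also stands. A reader might infer that the sparse-data rule in SAP 10.3 already covers the case, but that rule is written for the primary efficacy model and would need to be extended.

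Fourth, a reader might infer that household size matters more in this subset because the higher-count member is kept. The documents do not support that: baseline lesion count, the selecting variable, is in the model, and the simulation with selection built in showed no larger shift.

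**Conclusion.** The point holds as a small inconsistency in two supportive analyses. The one-per-household model omits a stratification factor that the primary model includes and that can still be estimated. The step 2 imputation regression omits a covariate of the model that analyzes the imputed data.

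Two stronger readings of the multiple imputation are tempting and wrong. A reader might infer that this analysis drops the stratum from the treatment comparison; it does not, because step 3 uses the primary model. A reader might also infer that imputed counts carry no household-size information. They carry whatever is in the baseline and Week 2, 4 and 8 counts used as predictors, and only the residual association is set to zero. Treatment is among the imputation predictors.

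The expected shift in the treatment log odds ratio is about 0.01 or less, against a standard error of about 0.17 in the one-per-household model. This rests on assumed numbers of two-subject households and assumed household effects. The simulated models in the table of step 4 of the working did not include investigator type, BOTE or age. No change in power or conclusion should be expected; the benefit is that both checks line up with the primary model.

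**What to change.** Before unblinding:

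1. SAP 11.1: add household size (one or two randomized subjects) to the one-subject-per-household logistic model.
2. SAP 10.4, step 2: add the same term to the imputation covariates.
3. SAP 10.3: state that the sparse-data removal rule also applies to the one-subject-per-household model.

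If either omission is intended, a sentence giving the reason would serve instead. The cost is one term in each of two models and one sentence. No new data are needed, and the sample size and primary analysis do not change.

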## 11.2 Secondary Efficacy Analyses

The secondary endpoints of the proportion of subjects achieving a lesion count of 0 or 1 of all treatable MC at Week 12, proportion of subjects achieving at least a 90% reduction from Baseline in the number of all treatable MC at Week 12, and the proportion of subjects with complete clearance of all treatable MC at Week 8 will be analyzed in the same manner as the primary endpoint.

Since the within-household correlation is expected to be small, the percent change from Baseline in the number of all treatable MC at Week 4 will be analyzed using a repeated measures mixed model for the respective visits with the same covariates as the primary model together with visits and treatment by visit interaction; an unstructured covariance matrix will be utilized. If the calculation of the percent change from baseline is influenced by outliers with calculated values >100%, then the influence of outliers will be avoided for analysis by censoring them so that all values were in the range of -100% to 100%. If the model fails to converge, then other correlation structures will be explored.

A sensitivity analysis using the PP Population will be provided for the proportion of subjects achieving a lesion count of 0 or 1 of all treatable MC at Week 12 and the proportion of subjects achieving at least a 90% reduction from Baseline in the number of all treatable MC at Week 12.

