## 6. GENERAL ANALYSIS CONSIDERATIONS

The statistical analyses will be reported using summary tables, listings, and figures (TLFs). The International Council for Harmonisation (ICH) numbering convention will be used for all TLFs. Unless otherwise noted, all statistical testing will be two-sided and will be performed at the 0.05 significance level. Tests will be declared statistically significant if the calculated  $P$ -value is  $\leq 0.05$ .

Continuous variable summaries will include the number of subjects ( $n$ ) with non-missing values, mean, standard deviation (SD), median, minimum, and maximum. Other statistics such as quartiles, confidence intervals (CIs), and number of missing values may be added as appropriate.

Categorical variable summaries will include the frequency and percentage of subjects who are in the category or each possible value. In general, the denominator for the percentage calculation will be based upon the total number of subjects in the study population within each treatment group, unless otherwise specified. The denominator for by-visit displays will be the number of subjects in the relevant study population with non-missing data at each visit.

All summary tables will be presented by treatment group. Baseline summaries will also include an overall summary column.

Individual subject data obtained from the eCRFs and any derived data will generally be presented by subject in data listings. Additionally, a listing of the subjects requiring a narrative because they experience one of the following events: serious adverse event, death, discontinued the study due to an AE, hypertrophic or keloid scarring, unresolved scars, or LSR suggestive of allergic contact dermatitis will be presented.

A separate report for the results from the study exit interview will be created.

The analyses described in this plan are considered a priori, in that they have been defined prior to breaking the blind.

Any analyses performed subsequent to breaking the blind will be considered post hoc and exploratory. Post hoc analyses will be labeled as such on the output and identified in the clinical study report.

All analyses and tabulations will be performed using SAS® software Version 9.4 or higher. Tables, listings, and figures will be presented in RTF format.

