## 8. ANALYSIS POPULATIONS

The following subject population will be used for disposition analyses:

- The Enrolled Population will consist of all subjects who have a signed informed consent or assent. If a subject is randomly assigned to a treatment, then treatment assignment will be based on randomized treatment; otherwise, they will be deemed a screen failure and will only appear in the overall summary columns of output.

The following subject population will be used for safety analyses:

- The Safety Population will consist of all subjects who receive at least 1 application of study treatment. Treatment assignment will be based on the treatment actually received. If a subject receives any amount of SB206, then they will be summarized in the SB206 10.3% QD arm.

The following subject populations will be used for efficacy analyses:

- The ITT Population will consist of all subjects who are randomized who have a signed informed consent or assent as applicable. Treatment assignment will be based on the randomized treatment.
- The Per-Protocol (PP) Population will consist of all subjects in the ITT Population who had no significant protocol deviations that impacted the analyses of efficacy endpoints. Final determination of subject inclusion in the PP Population will be made prior to unblinding. Treatment assignment will be based on the randomized treatment.

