### 10.7 Multiple Comparison/Multiplicity

The familywise error rate with respect to the primary endpoint and secondary endpoints will be strongly controlled at the  $\alpha=0.05$  level using a hierarchical fixed sequence method testing strategy in the order listed in Section 10.1. If the primary endpoint is not statistically significant at the  $\alpha=0.05$  level, the secondary efficacy endpoints will be considered not significant. If the primary endpoint is statistically significant at the  $\alpha=0.05$  level, then the secondary efficacy endpoints will be tested in the following hierarchical fixed sequence:

- 1) Proportion of subjects achieving a lesion count of 0 or 1 of all treatable MC at Week 12.
- 2) Proportion of subjects achieving at least a 90% reduction from Baseline in the number of all treatable MC at Week 12.
- 3) Proportion of subjects with complete clearance of all treatable MC at Week 8.
- 4) Percent change from Baseline in the number of all treatable MC at Week 4.

At each subsequent test of the secondary efficacy endpoints, if the secondary efficacy endpoint is not statistically significant at the  $\alpha=0.05$  level, the remaining secondary efficacy endpoints will be considered not statistically significant. If the secondary endpoint is statistically significant at the  $\alpha=0.05$  level, then the next subsequent secondary efficacy endpoint will be tested following the sequence.

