$$X_{H_{i11}} = \begin{cases} 1, & \text{if subject has a baseline age 7 to } <8 \\ 0, & \text{otherwise} \end{cases}$$

$$X_{H_{i12}} = \begin{cases} 1, & \text{if subject has a baseline age 8 to } <9 \\ 0, & \text{otherwise} \end{cases}$$

$$X_{H_{i13}} = \begin{cases} 1, & \text{if subject has a baseline age 9 to } <12 \\ 0, & \text{otherwise} \end{cases}$$

$X_{H_{i5}}$  is the subject's baseline lesion count; treatment will be included in the class statement with PARAM=REF and REF=Vehicle. The working correlation will have an exchangeable structure. In the event of issues with convergence, an independent structure will be utilized. The model will include a repeated statement for subject household with household ID in the class statement. Also, the data structure will be ordered according to household ID and subject ID in household.

Treatment groups will be compared using a generalized estimating equation for logistic regression with an exchangeable working correlation structure. The model will include treatment, investigator type (dermatologist vs other), household number of randomly assigned subjects (1 subject per household vs 2 subjects per household), BOTE score at Baseline (no inflammation [BOTE=0] vs mild/moderate/severe/very severe inflammation [BOTE≥1]), age (0 to <3, 3 to <4, 4 to <5, 5 to <6, 6 to <7, 8 to <9, 9 to <12, and ≥12 years old), and baseline lesion count as factors. For subjects from a household with 2 subjects, the actual values of BOTE score at Baseline and investigator type will be utilized with the recognition that such subjects did not have further stratification according to investigator type and BOTE score at Baseline. The odds ratio between SB206 10.3% and vehicle gel, 95% confidence intervals for the odds ratio, and *P*-value for the covariate-adjusted treatment comparison will be presented together with predicted proportions along with their associated 95% confidence interval. The difference in proportion confidence interval will be calculated using the following formula:

$$(p_{SB206} - p_{Vehicle}) \pm z_{0.025} * SE$$

Where the SE =

$$\sqrt{\frac{p_{SB206}^2(1 - p_{SB206})^2 s_{SB206}^2 + p_{Vehicle}^2(1 - p_{Vehicle})^2 s_{Vehicle}^2 - 2p_{SB206}(1 - p_{SB206})p_{Vehicle}}{(1 - p_{Vehicle}) * \left( \frac{s_{SB206}^2 + s_{Vehicle}^2 - s_{Odds Ratio}^2}{2} \right)}}$$

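### The Week 4 percent-change test, last in the fixed sequence, ignores household correlation and leaves its truncation rule conditional on an undefined trigger, so its 0.05 level is not guaranteed

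*SAP*

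**What the plan says.** **Design.** SAP 4 allows at most two subjects per household: "Households randomizing two subjects will receive the same treatment assignment for both subjects". These households form a single stratum "because the overall sample that is expected for the stratum for households with two subjects is not large enough to support further stratification".

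**Primary and first three secondary endpoints.** SAP 11.1 uses a logistic GEE with exchangeable working correlation: "The model will include a repeated statement for subject household with household ID in the class statement". SAP 11.2 applies the same analysis to the three binary secondary endpoints.

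**Week 4 percent change.** The method sentence in SAP 11.2 opens "Since the within-household correlation is expected to be small, the percent change from Baseline in the number of all treatable MC at Week 4". It then assigns a repeated-measures mixed model with the primary model's covariates, visit, treatment by visit, and an unstructured covariance. Household size (one or two subjects) is one of those covariates, but household does not enter the covariance. The one-subject-per-household sensitivity analysis in SAP 11.1 covers only the primary endpoint (Table 14.2.1.8), and the per-protocol analyses in SAP 11.2 do not include Week 4.

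**Truncation.** "If the calculation of the percent change from baseline is influenced by outliers with calculated values" above 100%, all values are to be brought within -100% to +100%. The SAP does not say what counts as influence, who decides, or when. Protocol 10.3.6 describes the repeated-measures model for percent change without any truncation.

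**Error control and timing.** SAP 10.7: "The familywise error rate with respect to the primary endpoint and secondary endpoints will be strongly controlled at the" 0.05 level. SAP 6: "The analyses described in this plan are considered a priori, in that they have been defined prior to breaking the blind", and anything done after unblinding is to be labelled post hoc. SAP 6 also has the database through Week 12 frozen and unblinded for the primary analysis, and the Week 4 data are in it. For the per-protocol set, SAP 8 fixes the timing: "Final determination of subject inclusion in the PP Population will be made prior to unblinding".

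**The concern.** Strong control must hold for every combination of true and false nulls. Suppose the first four nulls are false and the Week 4 null is true. The familywise error is then bounded by the size of the Week 4 test, and approaches it as the power of the earlier tests approaches one. So the claim in SAP 10.7 needs a valid Week 4 test.

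**Household.** When both members of a pair are in the same arm, positive correlation between them increases the variance of the treatment contrast. Household size as a fixed effect adjusts the mean and does nothing for this correlation. The standard error is therefore too small whenever the correlation is positive. The SAP dismisses the correlation without a figure or a check. For the Kaplan-Meier analysis in SAP 11.3 it adds that the endpoint is exploratory, a reason not available for a test inside the controlled family.

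**Truncation.** The trigger is likely to come into play. Eligible baseline counts start at 3, so a rise from 3 to 7 lesions is (7 - 3)/3 = +133%, and Protocol 2.1.2.1 warns that counts often rise early in treatment. With no criterion or date, the choice between truncated and untruncated results could be made after treatment labels are known.

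**Working it through.** **Inputs from the documents.** Two-sided test at 0.05 (SAP 6); 850 subjects, 425 per arm (SAP 5); households of at most two, both members in one arm (SAP 4). The plan states no power or variance for Week 4, so the only plan figure to test is the nominal 0.05.

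**Inputs assumed, because the documents give none.** Share of subjects in pairs, f: 5% to 30%. Within-household correlation, r: 0.1 to 0.5. Share of subjects above +100% at Week 4: 2.4% to 13.2%.

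**(a) Household term omitted.** For pairs in the same arm:

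- Design effect: DEFF = 1 + f × r
- True two-sided level = 2(1 - Φ(1.96/√DEFF))
- Variance understated by 1 - 1/DEFF

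Example: f = 0.20, r = 0.3 gives DEFF = 1.06, 1.96/√1.06 = 1.904, level 5.70%, variance understated by 5.7%.

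The last two columns are a simulation check: 20,000 null trials per case, 850 subjects, linear model at one visit with treatment and household size.

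| f | r | DEFF | Variance understated | Level, formula | Simulated, no household term | Simulated, household-clustered SE |
|---|---|---|---|---|---|---|
| 5% | 0.1 | 1.005 | 0.5% | 5.06% | 5.1% | 5.1% |
| 10% | 0.1 | 1.01 | 1.0% | 5.11% | 5.0% | 4.9% |
| 10% | 0.3 | 1.03 | 2.9% | 5.35% | 5.3% | 5.0% |
| 20% | 0.3 | 1.06 | 5.7% | 5.70% | 5.8% | 5.1% |
| 30% | 0.5 | 1.15 | 13.0% | 6.76% | 7.2% | 5.3% |

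Monte Carlo error is about 0.15 to 0.2 points. Over all simulations run, including others with different assumed distributions, the household-clustered level lay between 4.7% and 5.6%.

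**(b) Truncation rule.** 20,000 null trials per setting, 425 per arm, no clustering, baseline counts 3 to 70, Poisson counts with a log-normal ratio of SD 0.35, 0.5 or 0.7.

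| Subjects above +100% | Always truncate | Never truncate | Trigger on pooled blinded data | Better result, labels known | Same, favouring SB206 (nominal 2.5%) | The two results disagree on significance |
|---|---|---|---|---|---|---|
| 2.4% | 5.2% | 5.2% | 5.2% | 6.0% | 3.1% | 1.7% |
| 6.7% | 5.0% | 4.9% | 5.0% | 6.4% | 3.2% | 3.0% |
| 13.2% | 5.0% | 5.1% | 5.0% | 7.5% | 3.9% | 4.9% |

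A second simulation with log-normal lesion ratios (8,000 trials per setting) gave 6.6%, 7.4% and 8.0% for the labels-known choice when about 5%, 9% and 13% of subjects exceeded +100%. Adding the household omission at f = 20%, r = 0.3 raised these to 7.9%, 8.3% and 8.9%.

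**The case against.** **The household effect is negligible where the documents point.** The SAP calls the two-subject stratum small and expects little correlation, which suggests 5.06% to 5.11%. At f = 5% and 10% with r = 0.1, one simulation gave 5.09% and 5.21% without clustering against 5.05% and 5.16% with it, differences inside Monte Carlo error. The choice is disclosed and reasoned, and the sponsor holds data from two earlier phase 3 trials. This stands as to likely size. It does not supply the missing figure, and it does not explain why the other four tests in the family are clustered and this one is not.

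**Most of the truncation rule is fixed.** The affected values and the bounds are given; only the on/off condition is loose. Nothing plans a choice between results, and SAP 6 makes post-unblinding analyses post hoc. It is true that no such choice is planned. But both branches are within the plan, so the post hoc sentence would disqualify neither. If the intention is always to truncate, one sentence would say so.

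**Reach is small.** The test is last, and a false claim here first requires significance on the primary and three secondary endpoints. This stands.

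**The check uses a simpler model.** The simulations are linear models at one visit, not the planned repeated-measures model, so the figures show the order of magnitude. This stands too.

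**Conclusion.** The concern holds. The Week 4 test belongs to a family declared strongly controlled at 0.05, yet its covariance omits a dependence that the design creates and the SAP handles in the other four tests.

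For any positive within-household correlation the level exceeds 5%: by about 0.1 point at 10% in pairs and correlation 0.1, and by 1.8 points at 30% and 0.5. The low end is more likely, and the range rests on assumed values.

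The truncation clause does not by itself bias the test. Either fixed rule, or a decision on blinded data, keeps about 5%. It raises error to roughly 6% to 8% only if the choice is made knowing the treatment results; the combined 7.9% to 8.9% is a worst case, not a prediction. The defect is that the plan leaves such a choice open.

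The primary and secondary endpoints 1 to 3 are unaffected. This is worth correcting because the correction is nearly free, not because the likely error is large.

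**What to change.** Amend SAP 11.2 before the Week 12 freeze and unblinding.

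1. Use empirical (sandwich) standard errors for the Week 4 model with household ID, not subject ID, as the clustering unit. The unstructured visit covariance within subject and the mixed-model estimate can stay; contributions to the sandwich are summed over the household. A household random intercept is an alternative, but few pairs would identify it and it may worsen convergence.
2. Replace the conditional truncation sentence with one unconditional rule, for example that every value above +100% is set to +100%, with the untruncated model as a sensitivity analysis. Never truncating, fixed in advance, controls error equally well.

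The same paragraph leaves the fallback covariance open if the model does not converge. Listing the alternatives in order would complete the specification, though that is separate from the figures above. Carrying the method into SAP 11.3 is for consistency only, since those endpoints are exploratory.

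**Cost.** No new data: a small change to the model code and a short SAP amendment. The standard error grows by √DEFF - 1: √1.01 - 1 = 0.5% (10% in pairs, correlation 0.1) to √1.06 - 1 = 3.0% (20%, 0.3).
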